## 5.1. CONSENT PROCEDURE

#### 5.1.1.Potential participant with the capacity to give written consent

A Participant Information Sheet (PIS) will be provided to facilitate the process of consent. To avoid overwhelming patients already facing a life-threatening condition, a Summary PIS will be provided. Unless the full PIS is requested during consent, it will be provided later when the participant's condition has improved. The PI or delegate will ensure that they adequately explain the aim of the trial, trial intervention, and the anticipated benefits and potential hazards of taking part in the trial to the potential participant. They will also explain that participation in the trial is voluntary, and they can refuse to take part or withdraw from the trial at any time without affecting their care.

The potential participant will be given sufficient time to read the PIS, given the opportunity to ask questions, and, if desired, discuss their participation with others beyond the clinical or research team. If the potential participant then expresses an interest in participating in the trial, they will be asked to sign and date the latest version of the Informed Consent Form (ICF). The consent will document that the participant understands and acknowledges that a copy of the signed ICF will be transferred to the ERASER Trial Office for review. In situations where the potential participant has the capacity and has agreed to join the trial, but is unable to physically sign the ICF (e.g. unable to hold a pen), a witness will countersign the ICF (the witness does not need to be on the Site Signature and Delegation Log).

The PI or delegate will countersign and date the ICF. A copy will be given to the participant, filed in the medical notes and sent to BCTU, and the original placed in the Investigator Site File (ISF). Once the participant is entered into the trial, the participant's trial number will be entered on the ICF maintained in the ISF.

#### 5.1.2. Potential participant lacking capacity to give consent (for sites in England and Wales)

Participants that are eligible to be recruited into the ERASER trial will have suffered significant trauma and as a result may not have the capacity to provide written and informed consent at the time of hospital admission. In such instances, consent can be provided by a personal consultee (see section 5.1.3), or if one is not immediately available, a nominated consultee (see section 5.1.4).

#### 5.1.3. Personal consultee

A personal consultee is defined as a person who cares for the adult lacking capacity or is interested in that person's welfare, but is not doing so for remuneration or acting in a professional capacity.

If the potential participant lacks capacity, the PI or delegate should, in the first instance, seek advice from a personal consultee on whether the potential participant would wish to be included in the trial. A personal consultee is not asked to give consent on behalf of the potential participant but rather to provide an opinion on the views and feelings of the potential participant. They will be given sufficient time to read the Consultee/Legal Representative Information Sheet and provided with ample opportunity to ask questions and discuss with others beyond the clinical or research team.

The consultee must be informed that they are:

- Being asked to advise on the views and feelings they believe the patient would have towards participating in the ERASER Trial
- Free to decide whether they would like to provide this advice
- Provided with sufficient understandable information about the ERASER Trial so that they can provide informed advice

The advice given by personal consultees will be recorded on a Consultee Declaration Form. If/ when the participant regains capacity during the study, the PI or delegate will follow the procedure in section 5.1.6 and confirm ongoing consent.

#### 5.1.4. Nominated consultee

A nominated consultee is defined as a professional who is independent of the trial.

If a suitable personal consultee is not immediately available, advice from a nominated consultee can be recorded instead on the Consultee / legal representative Form. The nominated consultee must be informed on the points specified section 5.1.3.

If/ when the participant regains capacity during the study, the PI or delegate will follow the procedure in section 5.1.6 and confirm ongoing consent.

If the legal representative is of the opinion that participating in the ERASER Trial is not in the best interests of the potential participant, they will not be recruited into the trial and will be provided with usual care without prejudice.

#### 5.1.5. Potential participant lacking capacity to give consent (for sites in Scotland)

In Scotland, where a potential participant is unable to consent for themselves, consent can be provided by a legal representative.

The PI or delegate should ask a legal representative to provide consent on behalf of an adult who lacks capacity to do so themselves. Those who are able to act as a legal representative are patient's welfare guardian or welfare attorney, and if one is not appointed, the patient's nearest relative.

The legal representative must be informed that they are:

- Being asked to give consent on behalf of the incapacitated patient
- Free to decide whether they wish to make this decision or not
- Being asked to consider what the patient would want, and to set aside their own personal views when making this decision
- Given sufficient information, in an understandable form, about the ERASER Trial to ensure that they can make an informed decision

The consent given by the legal representative will be recorded on a Legal Representative Consent Form. If/ when the participant regains capacity during the study, the PI or delegate will follow the procedure in section 5.1.6 and confirm on-going consent.

#### 5.1.6. When participant regains capacity

Where the participant regains capacity, the research team at the site should seek consent from them, at the earliest opportunity, using the current ethically approved PIS and ICF (process outlined in section 5.1.1). The consultee or legal representative should be informed of this at the outset. Should the participant express a view that they no longer wish to take part in the ERASER trial, their opinion will supersede that of the consultee or legal representative.

## 5.2. CONSENT DOCUMENTATION

Details of the informed consent discussions with the participant, consultee or legal representative will be recorded in the participant's medical notes. This will include the date of discussion, name of the trial, a summary of the discussion, version number of the documents given to the participant/consultee/legal representative, and date consent/advice received. Where consent/advice is obtained on the same day that the trial-specific procedures are due to start, a note should be made in the medical notes as to what time the advice/consent was obtained and procedures started.

Electronic copies of the PIS and ICF will be available from the Trial Office and will be printed or photocopied onto the headed paper of the local institution.

## 5.3. ON-GOING CONSENT

At each visit, the participant's willingness to continue in the trial will be ascertained (through the participant, consultee, or legal representative as appropriate) and documented in the medical notes. Throughout the trial, the participant, consultee or legal representative will have the opportunity to ask questions about the trial.

Any new information that may be relevant to the participant's continued participation will be provided. Where new information becomes available which may affect the decision to continue, the participant, consultee or legal representative will be given time to consider, and if happy to continue, they will be re-consented. Re-consent will be documented in the medical notes. The participant's right to withdraw from the trial will remain.

## 5.4. PARTICIPANTS WHO DO NOT SURVIVE

The most challenging ethical consideration in this trial is related to the inevitable death of some participants. Advice (England, Wales and Northern Ireland) or consent (Scotland) will always be obtained prior the participant being randomised, however in some instances this may have been provided by a nominated consultee (England, Wales and Northern Ireland) or a legal representative

who is not related to the participant (Scotland). Actively seeking out and informing relatives of trial participation is transparent and avoids potential distress should they, in the future, discover that their relative had been involved in research. However, this will impose an additional emotional burden at a time of great distress (e.g., the immediate aftermath of the loss of a relative). Previous and ongoing emergency care studies have used passive information approaches, placing information in publicly accessible locations and in sites likely to be visited by relatives of the participants (hospitals, GP surgeries, the offices of the Registrars of Births and Deaths). Such information contains brief information about the trial and contact details for those wishing to seek further information. This allows a relative to make an individual decision as to whether to seek further information to find out if their relative was part of the trial. ERASER will take this approach and an ethically approved poster will be provided to sites to display (in appropriate locations), for this purpose.

## 5.5. CONSENT TO LINK ROUTINE HEALTH DATA

There is an additional, optional statement in the ICF/Declaration Form for the participant/consultee/legal representative to acknowledge that they understand that the ERASER Trial Office might in the future, for other related research, collect participant data available in NHS routine clinical datasets, including primary care data (e.g., Clinical Practice Research Datalink, The Health Improvement Network, QResearch) and secondary care data (Hospital Episode Statistics) through NHS Digital and other central UK NHS bodies. The participant/consultee/legal representative will acknowledge that they understand that the ERASER Trial Office might send the participant's name, address, date of birth and NHS number to the relevant national registry, and then for the national registry to link this to their data and send the information back to the ERASER Trial Office. The acknowledgement by the participant/consultee/legal representative will also allow access to other new central UK NHS databases that will appear in the future. This will enable the ERASER Trial Office (subject to receipt of additional funding via another grant application) to assess longer-term impact and health service usage data without further contacting the trial participants.

## 5.6. CONSENT TO BLOOD SAMPLE COLLECTION

Participant/consultee/legal representative will be asked to acknowledge that they understand a blood sample will be collected and stored for analysis as part of future ethically approved research. The blood sample will be spun and stored at the site until batch transfer at appropriate intervals to the laboratory at the University of Birmingham for storage.

# 6. RECRUITMENT, ENROLMENT AND RANDOMISATION

# 6.1. SCREENING AND IDENTIFICATION

All patients who have suffered blunt chest trauma with MRF admitted to ward and critical care will be screened daily for eligibility. The site research team, who form part of the patient's clinical care team, will review patient's medical records to ascertain whether the patient meets the eligibility criteria. This process may be assisted by the Research Nurses/Practitioners employed or who hold an honorary contract with the site.

A medically qualified doctor, or an appropriately qualified healthcare professional, who has been delegated the task on the Site Signature and Delegation Log will confirm eligibility before randomisation. Potential participants who are deemed eligible will be approached by their clinical care team for consent as described in section 5. The patient will then be randomised and baseline data will be collected.

Details of all patients approached about the trial will be recorded on the Participant Screening/Enrolment Log, which will include data on the number of patients meeting the inclusion criteria but not entered into the trial and reasons for non-enrolment. The Participant Screening/Enrolment Log will be kept in the ISF, and should be available to be sent to the ERASER Trial Office upon request.

## 6.2. RANDOMISATION

## 6.2.1.Randomisation System

Randomisation will be provided by a secure online randomisation system at the BCTU (available at https://bctu-redcap.bham.ac.uk), thereby ensuring allocation concealment. Unique log-in usernames and passwords will be provided to site staff that have been delegated the role of randomising patients into the trial as detailed on the trial Site Signature and Delegation Log. These unique log-in details must not be shared with other staff and in no circumstances should staff at sites access the system using another person's login details. The online randomisation system will be available 24 hours a day, 7 days a week, apart from very short periods of scheduled maintenance. If delegated site staff have lost their username or password, the ERASER Trial Office should be contacted directly via email or telephone using the contact details outlined on page 5 of the protocol. In rare instances that the database is unavailable, researchers can call the telephone toll-free randomisation service ([name]) Monday to Friday, 09:00 to 17:00 UK time, except for bank holidays, government guided closures and University of Birmingham closed days.

# Please note: it is expected that the primary route for participant randomisation will be via the online randomisation system.

## 6.2.2.Randomisation procedure

After eligibility for randomisation has been confirmed and informed consent has been received from the participant, consultee or legal representative, the participant can be randomised into the trial using the online randomisation system (see section 6.2.1). Randomisation forms, which contain fields outlining all of the necessary information, including inclusion and exclusion criteria, will be made available and may be used to collate the necessary information prior to randomisation. All questions and data items on the Randomisation form must be answered prior to randomisation; a Trial Number

will then be allocated. If data items are missing, randomisation will be suspended but can be resumed once the information is available.

Following randomisation, a confirmatory email will be sent to the PI, ERASER Trial inbox and the individual randomising the participant.

The site research team should add the participant to the trial Participant Recruitment and Identification Log, which links participants with their Trial Number. The PI must maintain this document securely in strict confidence and it must not be submitted to the ERASER Trial Office.

#### 6.2.3.Randomisation method

Participants will be randomised at the level of the individual in a 1:1 ratio to either the Intervention arm: SAP plus usual care or control arm: usual care only. A minimisation algorithm will be used within the online randomisation system to ensure balance in the intervention allocation over the following variables:

- Gender (male, female)
- Age (<60 years, ≥60 years)
- Centre (NHS Trust name)
- Pulmonary contusion (unilateral, bilateral)
- Rib fracture (displaced, non-displaced)
- Anatomical location of fracture (anterior, lateral, posterior)
- Presence of flail segment (yes, no)

To avoid the possibility of the intervention allocation becoming predictable, a random element will be included in the algorithm. Full details of the randomisation specification will be stored in a confidential document at the ERASER Trial Office.

#### 6.3. BLINDING

ERASER is an open label trial and is not blinded at the patient or investigator level. However, the trial will utilise a blinded end-point review committee (BERC) to assess the primary outcome to determine the rate of pneumonia 5 days after randomisation using CPIS and all available trial related clinical information.

#### 6.4. INFORMING THE PARTICIPANT'S GENERAL PRACTITIONER (GP)

With consent from the participant/legal representative or no objection from the consultee, the participant's GP will be notified that they are in the ERASER trial, using the trial specific ERASER GP Letter.

# 7. TRIAL INTERVENTION

#### 7.1. TRIAL INTERVENTION

Participants randomised to the control arm of the ERASER trial will receive the usual care for analgesic management for patients with MRF as per local standard practice. Whereas patients randomised to the intervention arm will receive SAP plus usual. In order to be adherent to the intervention arm of the trial, the SAP catheter has to be inserted for a **minimum of 24 hours**, if the catheter is removed prior to this, it should be classified as a failure of intervention and a change of status form should be completed accordingly. There is no trial mandated maximum duration for how long a SAP catheter should remain in place, both monitoring and removal should be in line with local standard practice.

#### 7.1.1.Usual Care

The current usual care for patients with MRF may consist of twice a day physiotherapy, multimodal analgesia (e.g. gabapentin, non-steroidal anti-inflammatories, opioids), incentive spirometry and rib fixation. The content of usual care may vary slightly across NHS Trusts, which reflects the real-world variation in standard practice.

#### 7.1.2.SAP

SAP catheter (CE marked and produced for peripheral nerve blocks) is inserted, under ultrasound guidance, in the lateral chest wall between latissimus dorsi and serratus anterior muscles in the midaxillary line. Local anaesthetic will be infused, using a continuous infusion pump, at a rate consistent with local standard practice. Depending on the patients body weight, concentration of long acting local anaesthetic and the duration of infusion, we recommend a rate of infusion between 5-25ml/hr.

It is expected that there will be some variation in the technical aspects of block insertion. This represents real-world variation in anaesthetic practices and will not contribute to bias as the randomisation procedure will ensure balance across groups by centre. Location and dose of anaesthetic will be captured on a CRF. The technique for insertion of SAP catheters, initial local anaesthetic bolus dose and maintenance regime will be according to local policy.

#### 7.1.3.Training on SAP

Each site will receive full training for implementing the SAP catheter. This will consist of a competencybased mandatory programme that includes:

- A competency questionnaire completed by principle investigators before enrolment as a site to confirm the understanding and ability to deliver this trial. The CI will review the completed competency questionnaire, and sign off to confirm site competency.
- Successful completion of an online E-learning package
- If required, 'hands-on' ultrasound scanning sessions of critical care and trauma patients facilitated by the trial team

<sup>3 https://www.learningapps.co.uk/moodle/xertetoolkits/play.php?template\_id=1965

All anaesthetics and analgesia will be taken from standard pharmacy stock and administered according to local policy. This trial does not fall under the Medicines for Human Use (Clinical Trials) Regulations 2004; segregated stocks for trial use and specific trial labelling are not required. Temperature monitoring should follow local pharmacy practice and deviations need not be reported to the ERASER Trial Office.

# 8. OUTCOME MEASURES

#### 8.1. INTERNAL PILOT TRIAL OUTCOMES

The outcomes for the internal pilot are as follows:

- 1. Confirmation of the projected recruitment rate as determined by the traffic light system
- 2. Appropriateness of the randomisation method
- 3. Adherence to the follow-up schedule

#### 8.2. MAIN TRIAL OUTCOMES

#### 8.2.1. Primary Outcome

New diagnosis of pneumonia, as agreed by a blinded end point assessment committee, 5 days after randomisation.

#### 8.2.2.Secondary Outcomes

The secondary outcomes for the ERASER trial are as follows:

- 1. Reduces pain
  - Numerical rating scale (0-10), recorded average every 4 hours on days 1 to 5, day 14 and before discharge.
  - Patient reported brief pain index (BPI) at 1 and 3 months post randomisation.
- 2. Improves ventilatory function
  - Incentive spirometry peak expiratory flow twice a day
- 3. Reduces the number of days ventilated and the requirement for invasive/non-invasive methods
  - Number of days ventilated
  - Type of ventilation invasive/non-invasive
- 4. Improves mortality
  - Mortality measured at 1 and 3 months post randomisation
- 5. Is safe and doesn't have unforseen Complications
  - Measured by SAEs review from randomisation until discharge
- 6. Impacts opiate consumption such as morphine and related compounds
  - Participant opiate consumption measured at discharge and 3 months post randomisation
- 7. Reduces length of hospital stay
  - Length of stay in hospital
  - Length of stay in critical care level two/three facility
- 8. Reduces hospital re-admission within 30 days of discharge
  - Measured by any hospital re-admission within 30 days of discharge

<sup>4 The blinded end point review committee will make their diagnosis based CPIS data and all available trial related clinical information

- 9. Impacts Patient-Reported Outcome Measures:
  - $\circ~$  EQ-5D-5L at 1 and 3 months post randomisation.
  - MRC dyspnoea scale at 3 months post randomisation.
  - o BPI at 1 and 3 months post randomisation.
  - SF-MPQ-2 at 1 and 3 months post randomisation

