## 1.2.3.Choice of intervention

In the CI's cross-sectional cohort study (11), SAP block provides comparable, adequate, and effective analgesia to epidural analgesia post-insertion. A 3-arm trial was considered comparing SAP against TEA/PA and opiates individually; however, the group decided against this because exclusively comparing SAP to TEA/PA would significantly reduce recruitment due to restrictions on TEA/PA

insertion due to coagulopathy, head and spinal injuries, comorbidities and use of anticoagulant medications. The current trial will allow better recruitment due to less stringent inclusion/exclusion criteria making the results more applicable and generalisable. This approach also optimises the chance that significant differences in pneumonia rates, mortality and length of stay are identified as the patients with the highest levels of injury and comorbid disease who may benefit most from SAP analgesia are not excluded (19, 20).

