#### 9.1.3. During hospital stay (Day 1 (from time of randomisation) until discharge from hospital)

The following data will be collected **daily** from the time of randomisation, in line with the routine collection of usual care data:

- Current medication (concomitant medication; analgesic medication; other medication/treatments)
- Lung function assessments.
- FEV1 and FVC to be collected twice per day
- Rating of pain (VAS) every 4 hours on day 1-5, then on day 14 and at discharge
- Body temperature
- SOFA
- CPIS Day 5 only
- CXR interpretations
- Tracheal secretion
- Oxygenation
- Rating of pain (VAS) every 4 hours on day 1-5, then on day 14 and at discharge
- Critical care minimal data set
- Intervention insertion date/time (only recorded on the date of insertion)
- Intervention removal date/time (only recorded on the date of removal)
- Failure of intervention (i.e. SAP Catheter could not be inserted or removed within 24 hours)
- Routine laboratory tests: (WBC, CRP, culture of tracheal aspirate)
- ICU and/or hospital admission status
- Organ dysfunction through use of the SOFA score
- Other medications or treatments required for MRF
- Adverse events
- Survival status
- Blood samples (see section 9.1.5)

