#### 9.1.4. After discharged from hospital (Month 1 and 3 from time of randomisation)

The following will be collected by the site research team after the participant has been discharged from the hospital:

- EQ-5D-5L
- Resource usage
- MRC dyspnoea scale at 3 months only
- BPI
- SF-MPQ-2
- Charleson Comorbidity Index
- Adverse events
- Survival status

These data can be obtained from the hospital's data management systems or via telephone interview with the participant.

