#### 9.1.5.Blood sampling for future research

In anticipation of future studies, blood will be collected and spun from participants who have provided consent (either for themselves or where consent/ an opinion has been sought from a legal representative or consultee). These samples will be taken within 24 hours of randomisation, day 5 ( $\pm$  24h) and day 14 ( $\pm$ 24h) if the participant is still admitted and at discharge. The blood sample should be stored at -80°C, and eventually shipped in batches to the laboratory at the University of Birmingham. Full instruction of sample preparation and shipment will be available in a separate Work Instruction.

	Screening	Baseline	Days during hospital			ital	At discharge	Months post- Randomisation	
Visit	-	Day 0	1-5	6-13	14	15+	-	1	3
Time window	$\leq$ 72 hours	$\leq$ 48 hours		Dail	у		± 6 hours from discharge	± 7 d	ays
Eligibility check	х								
Valid informed consent		х							
Relevant medical history		х							
Basic demographic data		х							
Charleson Comorbidity Index		х						Х	х
Current medication		х	х	х	х	х	Х	Х	х
Date & time of injury		х							
Covid-19 diagnosis and treatment		х							
ICU/Ward admission details		х	x	х	x	x	x		
Randomisation		х							
Intervention insertion			х						
Intervention removal			х	х	х	х			
Failure of Intervention		х							
Date of discharge							Х		
Routine physical exam:									
Pregnancy test		х							
Body temperature		х	х	х	х	х			
AIS		х							
Frailty score		х							
SOFA		х	х	х	х	х			
CPIS		х	х	х	х	х			

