#### 11.1.1. Case Report Form Completion

The CRFs will include, but will not be limited to, the following forms in Table 9.

Form Name	Schedule for submission
Consent form	As soon as eligibility has been confirmed
Randomisation form	At the point of randomisation
Hospital admission form and Baseline form	Immediately following randomisation (Day 0)
Daily Assessment	Daily until day 30 or discharge
1 month and 3 month Follow-up CRFs	1 month and 3 months post-randomisation
	If expedited: emailed within 24 hours of site research team
	becoming aware of event
Serious Adverse Event Form	
	If non-expedited: emailed within 4 weeks of site research
	team becoming aware of event
Dragnangy notification Form	As soon as possible after becoming aware of participant's
Pregnancy notification Form	pregnancy
Change of status Form	As soon as possible after the point of notification or death

Table 9: ERASER Trial CRFs

A CRF should be completed for each individual participant.

In all cases, it remains the responsibility of the PI to ensure that the CRFs have been completed correctly and that the data are accurate.

The trial Site Signature and Delegation Log will identify the research team members with responsibilities for data collection. The delegated staff should ensure the accuracy, completeness and timeliness of the data reported.

Data reported on each form should be consistent with the source data and any discrepancies will be explained. All missing and ambiguous data will be queried. Staff delegated to complete CRFs will be trained to adhere to trial CRF completion guideline.

The following guidance applies to data and partial data:

- Only CRFs provided by the ERASER Trial Office should be used
- Date format and partial dates all dates should be in the format of DD/MMM/YYYY
- Time format all times should be in accordance with the 24-hour clock
- Rounding conventions should be to the nearest whole number: number ending 5-9 to be rounded up; number ending 1-4 to be rounded down.
- Trial-specific interpretation of data fields
- Entry requirements for concomitant medications use generic names where possible
- Trial specific interpretation of data fields where guidance is needed, additional information will be supplied
- Repeat laboratory tests if a test is repeated, it is either to confirm or clarify a previous reading. Confirmatory tests should use the original test values
- Protocol and GCP non-compliances should be reported to the ERASER Trial Office on discovery

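### Pain on Day 14 is scored only in patients still in hospital, so a between-arm estimate there would compare groups selected by length of stay

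*Protocol*

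**What the plan says.** Secondary outcome 1 in section 8.2.2 has two parts: the 0-10 score, "Numerical rating scale (0-10), recorded average every 4 hours on days 1 to 5, day 14 and before discharge", and the Brief Pain Index (BPI) at 1 and 3 months.

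The collection rules for the 0-10 score are these:

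- Section 9.1.3, which covers the hospital stay up to discharge, schedules it as "Rating of pain (VAS) every 4 hours on day 1-5, then on day 14 and at discharge". It is called a VAS there; I take it to be the same rating.
- Table 1 marks it at baseline, in the in-hospital columns for Days 1-5 and Day 14, and at discharge. Months 1 and 3 are blank.
- Table 9 in section 11.1.1 has the daily form submitted "Daily until day 30 or discharge".
- Section 9.1.4, introduced by "The following will be collected by the site research team after the participant has been discharged from the hospital", contains BPI and SF-MPQ-2 but no 0-10 score, and begins at Month 1.

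On length of stay, outcome 7 in section 8.2.2 is worded "Reduces length of hospital stay". Section 1.2.3 says the design improves the chance that "significant differences in pneumonia rates, mortality and length of stay are identified".

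On analysis, section 14.2 applies intention to treat to all analyses in the first instance. Section 14.2.2 gives continuous outcomes an adjusted mean difference with a p-value. Section 14.2.4 outlines imputation for the primary outcome only and expects little missing data.

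**The concern.** A participant who goes home before Day 14 has no Day 14 pain score. Those who have one are picked out by length of stay, which is fixed after randomisation and which the trial expects the intervention to change. Applying the general rule of section 14.2.2 to these scores would give a mean difference between two differently selected remainders, not between the randomised groups.

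The likely direction can be stated. If patients in less pain go home sooner, and SAP brings more of them below the 14-day mark, those left in the SAP arm are on average the worse cases. SAP then looks worse on Day 14 pain than it is.

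The discharge score has a different weakness. It is taken at a different time after injury in each patient, and that time may itself depend on pain being controlled. If both arms leave hospital at a similar level of pain, a real benefit can fail to show.

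Pain is the first-listed secondary outcome. The statistical analysis plan can decide how to use the Day 14 scores, but it cannot recover scores that were never collected.

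**Working it through.** **1. Who has a score, by section**

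| Time point | Where collected | Who has a value |
|---|---|---|
| Days 1-5 | 9.1.3, Table 1 | Inpatients; lost after discharge if that comes before Day 5 |
| Day 14 | 9.1.3, Table 1 | Only those still admitted |
| Discharge | 9.1.3, Table 1 | Everyone discharged alive |
| Months 1 and 3 | 9.1.4, Table 1 (BPI, SF-MPQ-2; no 0-10 score) | All survivors in follow-up |

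The same conditioning is explicit for blood samples in section 9.1.5, where Day 14 sampling applies "if the participant is still admitted and at discharge".

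**2. The protocol's only sample-size figure**

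Section 14.1 (15% v 7.5%, 90% power, 5% two-sided) reproduces:

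n = [1.960·√(2 × 0.1125 × 0.8875) + 1.2816·√(0.15 × 0.85 + 0.075 × 0.925)]² / 0.075² = 370.9, that is 371 per group.

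The point does not depend on it. I use 371 only to turn proportions into counts.

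**3. Size of the Day 14 bias (illustrative)**

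The protocol gives no length-of-stay or pain-score figures, so every input here is an assumption:

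- log-normal stay, log-SD 0.7
- pain SD 2
- correlation ρ between pain and log stay
- no true effect of SAP on pain

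For median stay m, let c = ln(14/m)/0.7. The proportion still admitted is 1 − Φ(c). Mean pain among them exceeds the overall mean by 2ρ·λ(c), where λ(c) = φ(c)/(1 − Φ(c)).

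Central case (control median 10 days, SAP 20% shorter, ρ = 0.5):

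- Control: c = ln(14/10)/0.7 = 0.481; still admitted 0.315; λ = 1.127; 371 × 0.315 ≈ 117 patients.
- SAP: c = ln(14/8)/0.7 = 0.799; still admitted 0.212; λ = 1.367; 371 × 0.212 ≈ 78 patients.
- Spurious difference = 2 × 0.5 × (1.367 − 1.127) = 0.24 points against SAP.
- A true benefit of 0.50 would appear as 0.50 − 0.24 = 0.26.
- Standard error of this contrast ≈ 2·√(1/117 + 1/78) = 0.29.

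A simulation with 1,000,000 patients per arm also gave 0.24.

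Spurious difference against SAP at ρ = 0.5:

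| Control median stay | Stay 10% shorter | 20% shorter | 30% shorter |
|---|---|---|---|
| 7 days | 0.12 | 0.26 | 0.42 |
| 10 days | 0.11 | 0.24 | 0.39 |
| 14 days | 0.10 | 0.21 | 0.35 |

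The difference is proportional to ρ. In the central case it is 0.14 at ρ = 0.3, 0.34 at ρ = 0.7 and 0 at ρ = 0. With no effect on stay, c is the same in both arms and the difference is 0 whatever ρ is.

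**The case against.** Four arguments on the other side deserve weight.

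- **The protocol does not specify a Day 14 contrast.** Section 8.2.2 is a recording schedule, and section 14.2 is an outline that defers to a statistical analysis plan. This stands in part. How Day 14 is analysed may be settled there, but the protocol lists it as an outcome time point and does not collect it from discharged patients.
- **The pain outcome does not rest on inpatient scores alone.** A reader might infer that it does. The documents do not support that: BPI at 1 and 3 months is scheduled for discharged patients, and the 4-hourly scores give up to 6 × 5 = 30 readings over Days 1-5, when the block is most directly at work.
- **The discharge score is not a subset selected by stay.** A reader might extend the Day 14 argument to it. Everyone discharged alive is scheduled for one. Its fault is variable timing that may depend on the outcome.
- **Reversal of a real benefit is not shown.** At ρ = 0.5 a true 0.50-point benefit shrinks to between 0.40 and 0.08 over the table but keeps its sign. Passing zero needs the extreme assumptions stacked together (median 7 days, 30% shorter, ρ = 0.7: 2 × 0.7 × (1.939 − 1.517) = 0.59), and nothing in the protocol supports that combination.

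It is also fair that other injuries may drive stay independently of rib pain, which would lower ρ, and that in the central case the bias is smaller than one standard error.

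**Conclusion.** The point holds for Day 14. The 0-10 score is listed as an outcome there but exists only for patients still admitted, so a treatment estimate would not compare the randomised groups. The direction is against SAP if SAP shortens stay and patients in more pain stay longer. The size cannot be taken from the protocol: about 0.1 to 0.4 points is illustrative, and it is nil if either condition fails.

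The discharge score carries a separate and lesser caution about timing. Days 1-5 are affected only through discharges before Day 5, and BPI is not affected in this way. The primary outcome and the sample size are untouched. This is a correction worth making to one secondary outcome, not a threat to the trial's main conclusion.

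**What to change.** In section 8.2.2, name Days 1-5 after randomisation as the between-arm comparison for the 0-10 score. Analyse it with a repeated-measures model that includes all available scores, so that patients discharged before Day 5 still contribute. This relies on their unrecorded scores being predictable from the recorded ones, which should be stated. Report Day 14 inpatient scores and discharge scores descriptively, with the number of patients at each, and without a treatment-effect estimate.

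The cost is wording in the protocol and the statistical analysis plan. The downside is that two listed time points become descriptive.

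If a Day 14 comparison is wanted, collect one 0-10 score that day from every survivor, by telephone if discharged. With 412 per arm (824/2), a control median stay of 8 to 10 days and SAP 10-20% shorter, the number of calls runs from 412 × (0.685 + 0.736) ≈ 585 to 412 × (0.788 + 0.868) ≈ 682, before allowing for deaths and withdrawals. Sites already telephone participants at 1 and 3 months, so the calls are feasible, but the mode would differ between inpatients and discharged patients, and that should be recorded.
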